For all participants, measurements for environmental, physiologic and biochemical markers will be taken twice a week, and twice per day for a total of four data collection time points per week. This will include one work day per week (on the last work day of their work week) and on 1 day per week off from work. On work days measurements will be taken both immediately before (to establish pre-work biological parameters) and immediately after their work shift, and on non-work days measurement will be taken at approximately the same times during their day(s) off. In addition, blood pressure will be measured, data on heart rate variability will be downloaded, and a blood sample will be taken from each participant via finger stick to provide for measures of inflammatory markers and changes in white blood cell profiles. Salivary cotinine levels will also be measured twice (once at Intake and at the halfway point) for all participants to assess any exposure to smoking or smokeless tobacco products. High sensitivity C-reactive protein will be measured once during Intake and again at end of the 1 month period of participation. Buccal swabs will also be taken once during Intake for all participants, to measure epigenetic changes associated with inflammation, cancer and heart disease. Measurements will take place at locations most convenient for participants. Locations may include enclosed taxi garages, taxi relief stands, semi-private spaces within public venues, MSKCC offices or our community partner locations. Staff will not conduct any assessments at a participant's home. All measurements will be collected by trained study staff including both IHCD research and outreach personnel. Samples will be collected and transported immediately to MSKCC Core facilities, located on the 4th floor of the Breast and Imaging Center for storage. Samples will be shipped to NYU facilities for processing by Dr(s) [name] and [name] (see Lab Manual for shipping details). Trained study research and outreach personnel will be handling the specimens.

*Please see Appendix 4 RSA guide/lab manual for full details on all procedures.

1. PM values (measured daily):

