11.0 BIOSTATISTICS

Overview. This pilot study follows a two parallel arm design. Drivers will be randomized to one of two groups, an Intervention Group (an in-vehicle HEPA filter will be provided) and a Wait-list Control Group (HEPA filter will be provided at the end of wait-list period). We plan to recruit a sample of n=14 participants in each group (n=11 per arm with analyzable (non-missing) data, assuming a 25% drop-out rate as described below).

General analytic strategies. The general data analytic paradigm for this pilot study will be descriptive statistics only. The aim is to collect pilot data to help guide a future randomized intervention study. Descriptive statistics and assessments of correlations will be sought to address the aims (see below). The sample size of 14 per condition was primarily determined by resources limitations. A sample of 14 per condition was deemed possible within the funding resources of no more than 2 years.

Analytic plans for the Specific Aims.

Aim 1a: The primary aim will be to collect preliminary data on in-vehicle excess PM exposure.

Descriptive statistics (means and standard deviations) will be sought on: 1) PM size distribution 2) mass concentration, and 3) chemical composition for all three groups. These observations will be used to evaluate to what extent the two groups were exposed to these environmental hazards. For each study participant, an area-under-the-curve (AUC) summary will be sought for each of the three PM measurements over appropriate time periods. Generally, a daily average will be calculated from the hourly PM assessments. Then the AUC of the 28 daily averages will be calculated per person to represent the summary of PM exposures during study participation.

Aim 1b: To conduct a preliminary assessment of the correlation between PM exposure and physiologic and biochemical markers associated with increased risk of lung cancer and/or CVD.

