For each group, a correlation matrix will be constructed between the three components of the AUC outcomes described in Aim 1a and a set of physiologic and biochemical markers. Generally, Pearson's correlation coefficients will be sought. If preliminary analyses found the variables to be skewed, then Spearman's rank correlation coefficients will be calculated instead. The purpose of these correlation coefficients are to examine the associations between the environmental exposure to air pollutants and physiologic and biochemical markers. Point-biserial correlation coefficients will be sought between the continuous AUC summaries of PM data and other binary variables of interest (e.g., methylation). These correlation coefficients can be sorted in descending order to help identify the top candidates of physiologic and biochemical markers that are most likely to be associated with PM exposure. Care will be taken to match the variables by time, using the time stamps from the PM measurements and the date of biomarker serum collection. For example, the AUC of PM in the first week will be associated with serum cytokines measured during the first week. This work will have to be done in a post-hoc manner, after we have all data sources. Then we will evaluate the best strategies to link them together by time. It helps to have automatic time stamps by the PM measurement devices, which is likely to minimize coding errors and missing data.

Aim 2: To use a randomized wait-list controlled design to conduct a pilot study of whether a targeted intervention, installation of a portable car high-efficiency particulate air (HEPA) filter (to remove PM), results in a reduction of in-vehicle PM exposure and associated physiologic and biochemical markers among taxi drivers..

We will calculate the difference in the three PM components and in physiologic/biochemical markers between the HEPA intervention condition and the Wait-List Control condition to obtain the pilot data needed for a future, larger study with the potential to provide remediation to potential harmful exposures to air pollution among NYC taxi drivers.

Aim 3: To collect feasibility data on conducting the proposed randomized wait-list controlled pilot study among New York City taxi drivers.

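### Aim 1b, a primary outcome, rests on separate correlations in about 11 drivers per arm; a pooled, arm-adjusted estimate with intervals would be more precise at no data cost

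*Combined protocol and SAP*

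**What the plan says.** Section 9.1 gives two primary outcomes. The second is the preliminary correlation of PM exposure with physiologic and biochemical markers, and it names systolic blood pressure and HRV.

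Section 11.0 sets the frame: "The general data analytic paradigm for this pilot study will be descriptive statistics only". The sample size follows from resources, and the expected yield is "n=11 per arm with analyzable (non-missing) data, assuming a 25% drop-out rate". For Aim 1a an area-under-the-curve (AUC) "summary will be sought for each of the three PM measurements over appropriate time periods", and the general rule is one AUC of 28 daily averages per driver. For Aim 1b, "For each group, a correlation matrix will be constructed between the three components of the AUC outcomes described in Aim 1a" and the markers. The coefficients are Pearson, Spearman if the data are skewed, or point-biserial for binary markers. They may be sorted to find the leading candidates.

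Time matching is promised: "Care will be taken to match the variables by time, using the time stamps from the PM measurements". The one example pairs first-week PM with first-week cytokines. The method is left open: "This work will have to be done in a post-hoc manner, after we have all data sources".

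Data collection is richer than this analysis. Section 7.1 plans measurements "twice a week, and twice per day for a total of four data collection time points per week". Under its item 3, blood pressure is taken before and after one work shift and at similar times on one non-work day each week. Under item 4, HRV is recorded on waking and before bed every day. Section 4.2 says that drivers act as their own controls. Other markers are sparse: "Buccal swabs will also be taken once during Intake for all participants", and cytokines are taken in weeks 1 and 4 only.

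**The concern.** The pilot exists to guide a larger trial. For that, a reader needs the direction and rough size of each association and how uncertain it is. A coefficient from 11 drivers with no interval gives little of this. Splitting by arm also invites a comparison of two noisy numbers: arms with the same underlying association will often look different, and the sorted list inherits that noise.

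For HRV and blood pressure, both named in the primary outcome, the protocol collects many readings per driver, but section 11.0 names no estimator that uses more than one value per driver. The design's idea of drivers as their own controls is not carried into the Aim 1b analysis. No confirmatory test is at stake.

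**Working it through.** **The plan's own figure.** Section 11.0 gives 14 enrolled per arm and 25% drop-out: 14 × 0.75 = 10.5, rounded to 11. The stated 11 reproduces, and two arms give 22.

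**Readings per driver (section 7.1).**
- HRV: 2 per day × 28 days = up to 56.
- Blood pressure: 4 per week × 4 weeks = up to 16, on 4 work days and 4 non-work days.

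**Precision of a correlation.** The Fisher interval is tanh(atanh(r) ± 1.96 × SE), with SE = 1/√(n − 3), or 1/√(n − 4) when adjusted for arm. The documents give no expected r, so the values below are illustrations.

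| | 1.96 × SE | Limits at r = 0 | 95% CI at r = −0.5 |
|---|---|---|---|
| One arm, n = 11 | 1.96/√8 = 0.693 | ±0.60 | −0.85 to 0.14 |
| Pooled, arm-adjusted, n = 22 | 1.96/√18 = 0.462 | ±0.43 | −0.77 to −0.09 |

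These hold for Pearson coefficients. Spearman intervals are slightly wider.

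**Comparing arms.** On the Fisher scale, the difference between two arms has SE √(1/8 + 1/8) = 0.5. In 40,000 simulated pairs of arms of 11 with the same true r = −0.5, the two coefficients differed by more than 0.3 in 38%.

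**What a within-driver model must allow for.** Half of each driver's blood pressure days are work days, and in-cab PM applies only on those days. Daily PM may therefore largely separate work from rest, which can affect blood pressure in other ways. The following size check uses assumed values throughout:
- Total PM variance is 1, with within-driver share V between 0.3 and 0.7.
- A fraction s of that within-driver variance, between 0.3 and 0.7, is the work-day contrast.
- The true slope is −0.20, and work days raise the marker directly by 0.2 SD.

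With equal numbers of work and non-work days, coded ±0.5, the work-day difference in PM is 2√(sV). The covariance of PM with the work-day code is 0.25 × 2√(sV) = 0.5√(sV). Without a work-day term, the bias is 0.2 × 0.5√(sV)/V = 0.1√(s/V):
- s = 0.3, V = 0.7: bias 0.065, slope about −0.13.
- s = 0.7, V = 0.3: bias 0.153, slope about −0.05.

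Simulation with 22 drivers and 8 days agrees: −0.04 to −0.13. Adding the work-day term removes the bias but inflates the SE by about 1/√(1 − s), which is 1.20 to 1.83 (1.2 to 1.9 in simulation).

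**Which exposures are daily.** Under section 7.1 item 1, the DataRam logs PM level every day, while composition comes from time-averaged filters. Under item 2, black carbon may be sampled on as few as one shift in week 1 and one in week 4. A day-level model is therefore supported for mass concentration only.

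**The case against.** The strongest reply is that this is a preference. The plan is descriptive, sized by resources, and calls Aim 1b preliminary. Per-arm matrices are a reasonable description, because the filter is meant to change PM in one arm after week 2. The plan also promises time matching, allows PM summaries over suitable periods, and openly says that the linkage is still to be decided. Most of this stands. It rules out calling the plan wrong, and it rules out any demand for tests or power. It does not remove the case for intervals, which are part of describing an estimate meant to guide a later trial. Nor does it rule out pooling: both arms are under usual conditions in weeks 1 and 2.

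A second reply is that a within-driver model brings problems of its own: confounding by work day, no daily composition data, readings that precede the day's exposure, and a second blood pressure device. This also stands and shapes the fix.

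A reader might infer that up to 56 or 16 readings per driver would make the estimate many times more precise. The documents do not support that. They give no variance components or PM error. Simulated ratios of standard errors ran from about 1.5 to 16 across assumed values, and they compare a short-term slope with a between-driver slope, which are different quantities. For blood pressure, the low-end ratio of 1.51 becomes 1.51/1.2 = 1.26, or 1.51/1.9 = 0.79, once a work-day term is included.

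**Conclusion.** The point holds as a cheap improvement. A primary outcome is estimated only by per-arm correlations on about 11 drivers, with no pooled estimate, no interval and no estimator for the repeated HRV and blood pressure readings. Pooling with adjustment for arm narrows the limits around zero from ±0.60 to ±0.43. This assumes 11 analyzable drivers per arm and a broadly common association in both arms. In the intervention arm the 28-day summary also mixes weeks before and after the filter, so the pooled value belongs beside the per-arm values and does not replace them.

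Two stronger conclusions are not supported: that the planned analysis is invalid, and that time-matched association is missing. The gain from a within-driver analysis cannot be sized from the documents.

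**What to change.** In section 11.0, Aim 1b:

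1. Keep the per-arm matrices as description.
2. Add a pooled, arm-adjusted correlation (n about 22) for each PM–marker pair, and give 95% CIs.
3. As a secondary description for HRV and systolic blood pressure, specify a mixed model with:
   - a driver random intercept and driver-centred DataRam mass concentration;
   - arm, period and work-day/non-work-day terms;
   - robust or AR(1) errors.
4. State the exposure window before each reading. Waking HRV and pre-shift blood pressure, for example, should use PM recorded before that reading.
5. Flag blood pressure that participants measured themselves on the alternative device allowed in section 7.1 item 3.
6. Report the slope with its 95% CI, labelled as a short-term association, beside the between-driver correlation and with the share of missing days.

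Markers taken once or twice stay with the correlations. The cost is a few sentences and modest programming; no new data or visits are needed. The output becomes slightly more complex, and PM measurement error will pull the within-driver slope toward zero, which the report should say.

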One of IHCD's long-standing community based participatory research programs (CBPR) is the South Asian Health Initiative (SAHI), founded in 2004. [name] has led SAHI in several projects on cardiovascular disease (CVD) and cancer risk reduction (104): South Asians Engaging in Hypertension Awareness and Treatment, an NIH-funded RCT of the impact of linguistically and culturally appropriate educational materials on hypertension (105); Smokeless Tobacco Oral Pathology Prevention and Awareness Network (STOP PAAN) (103); and the Health Camp Project (106). In [name]'s —Drive By Readings study, over 100 taxi drivers were followed through their tuberculosis screening and treatment, with the results impacting TB policy in NYC (107). Additional taxi driver initiatives include: STEP I (Supporting Taxi Drivers to Exercise through Pedometers), funded by the NYS Department of Health Empire Clinical Research Investigator Program (ECRIP), to investigate the health knowledge, attitudes, and beliefs of South Asian taxi drivers. Drivers described high work-related stress, health risk, and poor health care access (21). STEP II, also funded by ECRIP, was a randomized controlled trial to evaluate the efficacy of a culturally responsive pedometer/motivational interviewing exercise intervention among taxi drivers (108). 74 male South Asian taxi drivers participated. 15% of the drivers who completed the study improved ≥ 2000 steps from their baseline (108). Step On It! is a cancer and CVD risk reduction case management project for NYC taxi drivers at John F. Kennedy airport, and a parallel effort in San Francisco in partnership with the Palo Alto Medical Foundation Research Institute (109). Airport holding lots are places where the taxi driver community can congregate to eat, talk, play games, walk/exercise, and pray. We have been successful in engaging the taxi driver community at airport holding lots in our risk reduction interventions. 480 taxi driver participants at JFK were enrolled in Step On It!, 50% of the taxi drivers did not have a primary care provider and 51% did not have health insurance prior to the intervention. 51% more are now engaged in ongoing care. 33% of the drivers were subsequently diagnosed with diabetes or hypertension and prescribed medication (109). CICHD facilitated the formation of the Taxi CAB (Community Advisory/Action Board) in 2010 to help further develop, implement, provide feedback to and context for results, and disseminate the taxi driver research program. The CAB has identified exposure to air pollution, and its impact on health, as an important issue for drivers. In [name] protocol X12-025, a pilot survey study to assess NYC taxi drivers' knowledge, beliefs and awareness of health risks associated with air pollution, 100 NYC drivers, including both yellow taxi (N=77) and livery (N=23) cab drivers, were surveyed. Sixty-seven percent of respondents had worked as drivers for at least three years, with 17% having worked more than 15 years. Drivers were evenly dispersed in age, with 17% between 18 and 30 years old, 24% between 31 and 40 years old, 26% between 41 and 50 years old and 32% over 50. Eighty-eight percent of all drivers were foreign-born. Over half of all surveyed drivers (56%) believed that they are exposed to more air pollution than those who are not taxi drivers, while 25% did not believe as such, and 19% were unsure. Most drivers thought that air pollution in general causes health problems (81%), while 19% did not agree or were unsure. A belief that air pollution causes health problems was significantly associated ($p < 0.05$) with drivers who had at least 10 years of taxi driving

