Physiologic and biochemical markers will be measured by trained study staff twice per week and twice per day on 1 work day and 1 non-working day per week, for a total of four measurements per week (see section 7 for details). Physiologic and biochemical markers to be measured include: high-sensitivity C-reactive protein, blood pressure, and reduced heart rate variability – data to be downloaded via a smart phone (associated with CVD), and pro/anti-inflammatory cytokines (i.e., interleukin (IL)-1b, -6, -8, -10, tumor necrosis factor (TNF)-α, and interferon (IFN)-γ), and epigenetic changes associated with cancer and/or inflammation (see Figure 1 below and section 7 for details).

[figure not shown]

Figure 1: DRIVe Phase 1 - participant recruitment, screening, testing, intervention timeline in years 1, 2, and 3.

Polycyclic aromatic hydrocarbon (PAH) exposures will also be assessed through measurements of the urinary metabolite 1 hydroxy pyrene. Drivers will be asked to give a urinary sample in the morning after several days of work. They will be provided with a 100 cc sterilized polypropylene container. (Urinalysis Cup Kit). This will be collected by the study team, protected from sunlight and transported to *BAIC* for storage in a -20 degree freezer. Samples will ultimately be analyzed using liquid chromatography-tandem mass spectrometry (LC-MS-MS) by collaborating facility City College of New York. PAH exposures will also be measured through PUF sampler sized 10 cm by 2.2 cm diameter (171). Drivers will monitor PAH through PUF sampler one work day every week. The PUF filter will be placed in the vehicle of the drivers at the beginning of their work shift and picked up at the end of their shift. The study team will transport the sampler to the collaborating facility City College of New York for analysis.

The study team will be trained on screening and recruitment procedures, downloading DataRam results on PM measurements, on fingerstick blood, salivary, and buccal swab sampling procedures, and on storage/handling of samples (e.g. shipping dangerous goods training). Samples collected will be transported immediately by study staff to NYU for storage and analysis. If any critical abnormal/irregular health measurements are identified in the process of data collection, study staff will be trained to refer participant to low-cost health services.

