5.1 Subject Inclusion Criteria

Drivers:

- Full-time New York City cab drivers;
- Non Smokers (assessed by modified BRFSS smoking question within screening tool)
- Male;
- Between the ages of 21 and 90;
- No immediate plans (within the next 3 months) to leave the City for vacation or for trips back to their home country,;
- Driver for at least 3 years;*
- Driving schedule does not include overnight shifts, nor does driver have an additional job overnight;
- Own a smart phone (in order to collect heart rate variability data)
- Should self-report —Very welllll or —Welllll level of English fluency (according to the standard US census question).
- Have working cigarette lighter receptacle/socket inside taxi cab

**The requirement to have worked at least 3 years in the U.S. should minimize any acute health effects/disease due to high levels of contaminants associated with country of origin.*

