Following informed consent, participants will be assigned a participant number and administered the Intake Assessment (Appendix B). Participant drivers will also be randomized to either the Intervention or Wait-list Control Groups, as described above. A convenient time and place will then be arranged to complete the informed consent and Intake. Driver pairs will participate in the study in approximately the same time frame to avoid seasonal differences in PM levels.

During consent procedures, participants will be informed that they will receive a \$200 incentive over the course of the study for their participation to account for the time commitment required of participants. This will be distributed as 4 weekly incentives totaling \$50.00 each, which can be viewed as compensating study participants \$7 each day for carrying around monitors throughout their daily lives and allowing us to conduct biologic assessments 2 days a week. All participants will also be informed that they will receive a HEPA air purifier. Given the intensity of the proposed study measurements and the

associated time required of participants, for which drivers could result in lost earnings, the \$200 incentive is commensurate with the degree of commitment demanded.

Consenting professionals will emphasize the need to meet with participants 2 days a week to conduct study testing, and will discuss and compile a list of 2-3 future meeting locations for data collection. Convenient locations may include enclosed taxi garages, taxi relief stands, semi-private spaces within public venues, MSKCC offices or our community partner locations. Staff will not conduct any assessments at a participant's home.

During the initial conversation between the investigator/research staff and the potential study participant, the potential participant may be asked to provide certain health information that is necessary to the recruitment and enrollment process. They will use the information provided by to confirm that the potential participant is eligible and to contact the participant regarding study enrollment. If the person turns out to be ineligible for the research study, the research staff will destroy all information collected on the patient during the initial conversation, except for any information that must be maintained for screening log purposes.

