7.1 ASSESSMENT/EVALUATION PLAN

All potentially eligible participants will be required to complete a study screening tool to confirm eligibility. Participants that undergo informed consent procedures will be required to complete an intake assessment to gather details on personal demographics and health information that may relate to study outcomes. Enrolled drivers will be provided a log to compile a detail account of vehicle air-flow conditions while driving during study participation.

Screening tool (Appendix A), a brief questionnaire administered to potential to assess if study eligibility requirements are met. Includes questions on age, residence, country of origin, previous travel and travel intentions, modified BRFSS tobacco use classification questions (160); English proficiency, smoking status, cab driving experience, current occupation(s), and status of pre-existing conditions relevant to study (e.g. sleep disorders, autoimmune conditions). (5 min to complete)

Intake assessment (Appendix B) administered to all study participants includes 3 sections of questions: (1) demographic and health access information, (2) medical history and (3) physical activity and nutrition. (10-15 min to complete)

Log-book (Appendix C), given to drivers to record environmental manipulations within the area they are driving or their vehicle. This includes air exchange levels within the cab (documenting whether the DataRam is used, HEPA filter and air conditioning is on, vents and windows are open, the vehicle make or model of taxi cab or the neighborhoods driven in during shift). This also includes documenting neighborhoods travelled thru, whether they were in high traffic jams, or travelled thru tunnels. In our preliminary work (X12-021), we have succeeded in encouraging drivers to complete a similar log-book. When we meet with drivers to conduct biological measurements, or contact them for any other reason, we will remind them to complete their log-books using the text reminder system described below.

During biological assessments (2 days per week), the make and model of the vehicle used by driver participants will be logged by study staff to account for variances within the current air filtration systems of the cab, because taxi drivers may rent different vehicles each day.

Environmental Measurements, Physiologic and biochemical markers

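### Aim 1b plans only unadjusted correlations between drivers within each arm, so age or season can contribute to a marker's rank if they are also related to PM; adjusted and within-driver estimates should be shown beside them

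*Combined protocol and SAP*

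**What the plan says.** Section 9.1 lists the correlation between PM exposure and the physiologic and biochemical markers as a primary outcome. Section 11.0 describes the analysis.

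- **Method.** "Generally, Pearson's correlation coefficients will be sought", with Spearman for skewed variables and point-biserial for binary markers such as methylation.
- **Unit.** "For each group, a correlation matrix will be constructed between the three components of the AUC outcomes". Each driver contributes one AUC over 28 daily PM averages. A week-specific AUC is offered as an example of matching exposure to a marker in time, with the linkage to be settled after the data are in.
- **Purpose.** "The purpose of these correlation coefficients are to examine the associations between the environmental exposure to air pollutants and physiologic and biochemical markers". The coefficients can be put in descending order to help pick out the markers most likely to be linked to PM.
- **Covariates.** None is named: no age term, no season term, no partial correlation.

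Other sections bear on this. Section 5.1 admits drivers "Between the ages of 21 and 90". Section 6.0 runs driver pairs at about the same time "to avoid seasonal differences in PM levels". Section 7.1 has an intake assessment to "gather details on personal demographics and health information that may relate to study outcomes". Section 4.2 says drivers act as their own controls, before and after work and before and after the intervention. Section 11.0 also declares the whole analysis descriptive.

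**The concern.** A correlation across drivers compares different men, so whatever differs between them and relates to both PM and the marker enters the coefficient. Two such factors are visible in the protocol.

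- **Age.** The eligible range is very wide. The sponsor's own survey of 100 drivers (Section 3.0, preliminary studies) found 17% aged 18 to 30 and 32% over 50.
- **Season.** The protocol accepts that PM varies by season. Pairing in time helps the comparison of arms if each pair has one driver in each arm, which is not stated. It does nothing for a correlation within an arm, where the drivers come from different pairs and so from different calendar times.

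The intake data that could address age are collected but not used in Section 11.0. The design also yields repeated measurements on each driver, yet Aim 1b specifies no within-driver analysis. What is at stake is how the candidate list is read: a marker may stand high partly because it tracks age or season.

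**Working it through.** **Sample size for Aim 1b.** Section 11.0 recruits 14 per arm and allows 25% drop-out: 14 × 0.75 = 10.5, rounded up to 11 analysable. This reproduces the plan's figure. Because the matrices are built per group, the relevant n is 11; pooling both arms would give 22.

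**Sampling noise alone.** By Fisher's z, the 95% limits for an unrelated marker are tanh(1.96/√(n − 3)).
- n = 11: tanh(1.96/√8), about ±0.60.
- n = 22: tanh(1.96/√19), about ±0.42.
- An observed r of 0.3 at n = 11 has an interval of about -0.37 to 0.76.

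**Spurious correlation from one common cause.** If PM has no effect on the marker, the expected r is r(age, PM) × r(age, marker). The documents give neither input, so these are assumptions: r(age, marker) = -0.5, and r(age, PM) from -0.3 to +0.4.
- (-0.3) × (-0.5) = 0.15
- (+0.4) × (-0.5) = -0.20

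The average sample coefficient is slightly nearer zero. Simulation under no PM effect gives:

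| n | r(age, PM) | mean unadjusted r | SD unadjusted | passing nominal 5%, unadjusted | SD age-partial | passing, age-partial |
|---|---|---|---|---|---|---|
| 11 | -0.3 | 0.14 | 0.31 | 7% | 0.33 | 5% |
| 11 | 0 | 0.00 | 0.32 | 5% | 0.33 | 5% |
| 11 | +0.4 | -0.19 | 0.31 | 9% | 0.33 | 5% |
| 22 | -0.3 | 0.15 | 0.22 | 10% | 0.22 | 5% |
| 22 | 0 | 0.00 | 0.22 | 5% | 0.22 | 5% |
| 22 | +0.4 | -0.20 | 0.21 | 14% | 0.22 | 5% |

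The 5% cut is only a yardstick; the plan sets no alpha. If age is unrelated to PM there is no bias, and adjustment costs almost nothing.

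**Effect on the ranking.** This run assumes 20 markers: one truly related to PM (r = 0.4), six driven only by the confounder (r = 0.5), and 13 pure noise. The confounder-PM correlation is 0.3, 0.5 or 0.7.
- A confounder-only marker comes first, n = 11: 29%, 38% and 53% of runs unadjusted, against 24% with no confounding and 26-27% after adjustment.
- The same, n = 22: 29%, 47% and 67% unadjusted, against 17% with no confounding and 20-25% after adjustment.
- The true marker comes first, n = 11, over all scenarios from no confounding to 0.7: 14-21% unadjusted and 12-19% adjusted.

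Adjustment removes most of the excess due to confounding, but at n = 11 it does not make the true marker easier to find.

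**The case against.** The strongest reply is that this is a descriptive pilot with no alpha and no power claim, and that noise swamps the bias: at n = 11 the spurious mean of 0.14 to -0.19 is about half the coefficient's SD of 0.31. That stands, and it limits the weight of the point. It does not remove it, since the list is meant to indicate markers linked to PM, and bias does not shrink as the follow-on study grows.

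It is also fair that age matters only if it is related to PM, which no section shows. Eligibility narrows one route: drivers must be full-time, with no overnight shifts and no overnight second job. Section 5.2 also controls several other influences by exclusion, including smoking, smoking households, sleep disorders, cancer, and inflammatory and serious cardiopulmonary disease. Age and calendar time are not restricted in this way.

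Three stronger readings are tempting but not supported.

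- **New medication mimicking a PM or filter effect.** Section 4.3 says that, for critical abnormal readings, "study staff will be trained to refer participant to low-cost health services", and Section 3.0 reports of an earlier programme that "33% of the drivers were subsequently diagnosed with diabetes or hypertension and prescribed medication". That programme was case management, with no time frame given, so the 33% cannot be carried into a 28-day study. Nothing links new medication to PM, both arms are randomised under the same referral rules, and the visit forms are in appendices not available here.
- **Enrolment spread over two years.** Two years is the whole project, including dissemination (Section 4.2); no enrolment window is stated.
- **The ranking decides the next trial's markers.** Section 11.0 says only that the coefficients can be sorted to help identify candidates.

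**Conclusion.** The point holds as a limit on how the Aim 1b coefficients can be read, not as an error in a test. The planned correlations are unadjusted, between drivers and per arm. Age is open from 21 to 90, and season is not handled within an arm. Under the assumed age correlations, 7-9% of null markers would pass a nominal 5% cut at n = 11 per arm, or 10-14% if 22 drivers were pooled, against 5% with age partialled out. These figures depend on an age-PM relation that the documents do not give; with none, the excess is zero. No size can be put on season from the documents. Sampling error remains the larger problem for any ranking, whatever is adjusted. The change is still worthwhile because it uses data already being collected and costs little.

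**What to change.** In Section 11.0, keep the planned coefficients and add two analyses beside them.

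1. **Markers measured repeatedly (blood pressure, HRV, cytokines).** Estimate within-driver associations with week-matched PM, centred on each driver's own mean. Use a mixed model with a driver intercept, terms for arm and period, and a term for work versus non-work day where both are sampled. This removes age and most of season, and uses the own-control feature that Section 4.2 already names.
2. **Markers measured once (methylation at Intake).** Report partial rank correlations pooled over arms and adjusted for age and arm. The arm term is needed because the Intervention group's 28-day AUC includes two weeks with the filter. Add calendar season as a sensitivity run.

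Give an interval with every coefficient, and state that at this sample size noise dominates any ordering, so rank alone should not be read as evidence.

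The cost is wording in Section 11.0, a little more analysis work, and one to two degrees of freedom. For age alone, the coefficient SD goes from about 0.21 to 0.22 at n = 22, and from about 0.31 to 0.33 at n = 11.
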